10.1 Summary of Withdrawal Options and Follow-Up Actions

In all cases participants will be followed up following RODEX visit/assessment schedule unless participant also explicitly withdraws their consent to do so, or other reason marked with an asterix (*) below.

Withdrawal	Primary Reason	Decision can be made by		ade by	Comments
From Trial		Patient	Local	Sponsor	
Treatment			Investigator		
Intervention	No response - treatment failure		X	X	Withdraw from ROM only, DEX only, or ROM + DEX
					Participant still followed up following RODEX visit/assessment schedule
	Patient choice	Χ			
	Adverse Event (AE)		X	X	AE will be followed up until AE resolved/stabilized. Complete and submit SAE notification form if considered an SAE.
	Intercurrent illness or worsening of a chronic condition		X	X	
	Diagnosis no longer ITP		X	Х	
	Pregnancy		Х		Female participants who become
	Intention to become pregnant	X	X		pregnant within 1 month of stopping treatment to be given pregnancy PIS/ICF and asked to provide optional consent for collection of pregnancy data. Complete and submit pregnancy notification form only if optional consent provided.
	Breastfeeding (lactation)		Х		Notify Sponsor/CTR by email. No separate data collection form or
	Intention to breast feed (lactate)	Х	Х		consent form to complete.
	Death *		Х		Complete death eCRF, and other relevant eCRF up to date of death.
	Lost-to-follow up *		X		If repeatedly fails to attend scheduled visits and is unable to be contacted by the study site following three telephone call attempts (where possible). Calls must bet documented in medical notes. Complete relevant eCRF up to date of lost-to-follow up.
	Patient non- compliance with treatment schedule		Х	Х	Report as a patient non- compliance
	Non-compliance with Protocol and/or study procedures		X	X	Report as a study non-compliance

Withdrawal From	Primary	Decision can be made by		Comments	
Other Trial Activities	Reason	Patient	Local Investigator	Sponsor	
Questionnaires					
SF-36 QOL	Other – e.g.	Χ			Report as a subject non-
FACTIT QOL	excessive	Χ			compliance if not returned
ITP PAQ QOL	burden	Χ			
ITP BAT		Χ			
Further study visits/assessments *		X			Report as a subject non- compliance if not attended unless participant deceased or lost-to-follow up
Further non-routine blood sample collection *		X			Report as a subject non-compliance.

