					Any non-routine blood samples collected to provide study assessment data must be destroyed immediately following assessment following local destruction procedure and destruction evidenced in hospital notes and TSF and notified to CTR to meet UK HTA regulatory requirements.

Withdrawal from	Primary	Decision can be made by			Comments
Data Use	Reason	Patient	Local	Sponsor	
			Investigator		
Use of data already collected from	Other	X			Report as a protocol non- compliance. Note: data
medical					already entered onto EDC
notes/systems for					cannot prior to withdrawal
RODEX study					will not be destroyed.
purposes					
Further data collection from medical notes/systems following withdrawal *	Other	X			Report as a protocol non- compliance and stop participant treatment.
Use of data for future research	Other	X			

Withdrawal From	Primary	Deci	ision can be mad	le by	Comments
Whole trial	Reason	Patient	Local	Sponsor	
			Investigator		
	Screening		Х	Х	Patient can be re-screened
	failure -				once only.
	eligibility				
	criteria not				This type of withdrawal is not
	fulfilled				permitted once the patient
					has been randomised.
					Eligibility issues identified
					after randomisation must be
					reported as a study non-
					compliance.
	Non-		X	Х	Specify reason
	compliance				
	with Protocol				
	and/or study				
	procedures				
	Urgent Safety		X	X	Specify reason
	Measure				
	Early			Х	Specify reason
	termination				
	of study				
	Temporary			X	Specify reason
	suspension				
	of study				
	Other	X	X	X	Specify reason

Withdrawal From	Primary	Decision can be made by		Comments	
Provision of	Reason	Patient	Local	Sponsor	
mother/child			Investigator		
pregnancy reporting	Other	Χ			Only if consent provided via
data					UK Pregnancy ICF consent is
					withdrawn for any reason

11 Trial Intervention

See Spanish Protocol for treatment supply, storage and dosing, concomitant medication, rescue

medicine, study treatment stopping and dose adjustment rules, and other trial restrictions, including

pregnancy, lactation, breastfeeding, contraception.

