12.1 Study visits, assessments, and samples

No urine samples will be collected above and beyond those collected for UK routine care.

Routine blood sample collections, visits, and assessment requirements vary for the UK RODEX patient

cohort dependent on local hospital differences in ITP-treatment practices permitted under UK NICE

ITP Treatment guidance: https://bnf.nice.org.uk/treatment-summaries/immune-thrombocytopenic-

purpura/. The number and frequency of study-specific visits for the collection and assessment of

RODEX trial-specific blood samples will be marginally higher than routine care at most, and vary across

different, UK participating sites.

SOECAT costs associated with routine and research visits, assessments and samples are based on local

practice at the lead UK participating site (University Hospitals Bristol and Weston NHS Foundation

Trust); collection of up to three new blood samples above and beyond routine care from participants

assigned to Arm A (ROM+DEX) only during weeks 9-15 for clinical trial assessment purposes only.

Local differences to the lead UK Site procedure must be documented on the site registration form and

discussed with the UK National Coordinator prior to site set up and site green light approval.

All research and/or routine samples will not be transferred outside of the collecting host NHS

organisation and will be destroyed immediately following analysis following local policies and

procedures.

Page 25 of 40

RODEX UK Protocol Addendum V2.0 17.08.2023 FINAL Authorised CLEAN TPL/003/1 v5.0, 26/10/2022

Responsibility for sample collection resides with the Sponsor. For avoidance of doubt, the research will be registered on the UK National Coordinator's Human Tissue Authority (HTA) Register (Holding Number: 702).

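### Declining only research bloods takes a participant off scheduled follow-up (section 10.1), which could cause avoidable, arm-related missing outcomes in the UK

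*Protocol*

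**What the plan says.** The rule above the tables in section 10.1 has a default and two exceptions. The default is "In all cases participants will be followed up following RODEX visit/assessment schedule". The exceptions apply where the "participant also explicitly withdraws their consent to do so, or other reason marked with an" asterisk.

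The asterisked rows are death, lost to follow-up, "Further study visits/assessments", "Further non-routine blood sample collection" and, in the data-use table, "Further data collection from medical notes/systems following withdrawal". There is no asterisk on stopping treatment by patient choice or on declining the SF-36, FACIT, ITP-PAQ or ITP-BAT.

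Section 10 asks sites to record which aspect of the trial a participant is leaving. It refers to Main Protocol Section 8, which is not available here, for the full rules on withdrawal and on data collection afterwards.

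Section 12.1 describes the non-routine samples: up to three beyond routine care, from participants "assigned to Arm A (ROM+DEX) only during weeks 9-15 for clinical trial assessment purposes only". This is a costing based on practice at the lead UK site, and the same section says that sampling and visits vary between UK hospitals.

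**The concern.** The two exceptions are joined by 'or'. An asterisk therefore ends scheduled follow-up by itself, even if the participant is willing to keep attending. For death that is self-evident. For someone who objects only to a few extra blood draws it is not: this participant would leave the schedule, while one who refuses all further trial drug would remain on it.

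What is at stake is the primary outcome, which needs at least 180 days from treatment cessation and freedom from WHO grade 2 or worse bleeding. If the extra samples are taken in the romiplostim arm only, this exit has no counterpart in the dexamethasone arm. Outcomes missing by this route could then be related to arm. Counting them as failures would lower the romiplostim rate, and dropping them would weaken the randomised comparison. The loss is avoidable, and analysis cannot fully repair it.

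**Working it through.** **1. Consistency of the table.** Under the rule in section 10.1:

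| Participant declines | Asterisk | Stays on visit schedule |
|---|---|---|
| Trial treatment (patient choice) | no | yes |
| Any questionnaire or ITP-BAT | no | yes |
| Non-routine bloods only | yes | no |
| Further visits/assessments | yes | no (unavoidable) |
| Records-based collection | yes | no |

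The third row is the anomaly. Bloods and visits are separate rows, yet the asterisk makes refusing the first act like refusing the second. That conflicts with the principle in section 10.

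**2. Timing.** Week 15 ends at about day 15 × 7 = 105, counting from the start of treatment (an assumption, as section 12.1 does not give the origin). The endpoint needs at least 180 days after cessation, so it cannot be observed by day 105 even if treatment stopped at once. The month 6, month 12 and end-of-study visits listed in section 3.3 all come later. Anyone who leaves by this route in weeks 9-15 leaves before the scheduled endpoint assessment.

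**3. Size.** The document gives no decline rate and no figure to reproduce. Inputs from the Synopsis: 126 participants in total, 26 or more in the UK. Assumptions: exactly 26 in the UK and 1:1 allocation, hence 63 per arm and 13 UK participants in the romiplostim arm.

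- UK share: 26/126 = 20.6%.
- If a fraction f of the 13 declines, the loss is 13f people, or 13f/63 of the romiplostim arm.
- If all of these count as failures and the true romiplostim rate is p, the observed rate falls by p × 13f/63. An assumed p of 40-70% gives the last column.

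| f (assumed) | People lost | Share of romiplostim arm | Fall in observed rate |
|---|---|---|---|
| 10% | 1.3 | 2.1% | 0.8-1.4 points |
| 20% | 2.6 | 4.1% | 1.7-2.9 points |
| 100% (ceiling) | 13 | 20.6% | 8.3-14.4 points |

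**4. Power, for illustration only.** Assume 35% vs 60%, two-sided alpha 0.05 and 63 per arm. Power = Φ[(d − 1.96 × SE0)/SE1], where d is the difference in rates, SE0 uses the pooled rate and SE1 the separate rates.

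- No loss: Φ[(0.25 − 1.96 × 0.0890)/0.0861] = 81.0%.
- f = 20%, cases simply missing (60.4 in the romiplostim arm): 80.2%.
- f = 20%, cases counted as failures (romiplostim rate 0.60 × (1 − 2.6/63) = 57.5%): 72.3%.

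The failure scenarios assume that nothing can be recovered from hospital records, so they show the unfavourable end.

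**The case against.** The strongest reply is that the asterisk governs the visit schedule, not all data. Stopping collection from hospital records is a separate option, so routine platelet counts, treatments and bleeding could still be obtained from someone who declined bloods. The comments column also treats refused bloods and missed visits as non-compliance, which fits a participant who is still in the trial. Section 10.1 is only a summary, and Main Protocol Section 8 may settle the matter.

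Much of this stands, and it limits the size of the problem. It does not remove it. Continued record collection is a fair inference, but section 10.1 never states it, and the lost-to-follow-up comment, "Complete relevant eCRF up to date of lost-to-follow up", suggests that entry stops. If Main Protocol Section 8 keeps these participants in follow-up, the UK table contradicts it. If it does not, the gap extends beyond the UK. Either way the row needs reconciling.

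A reader might infer three stronger points that the documents do not support:

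- **That the further-visits and lost-to-follow-up asterisks are also errors.** Scheduled visits cannot continue for someone who refuses them or cannot be found. Lost to follow-up requires both repeated missed visits and no contact after three telephone attempts (where possible), so an unanswered telephone alone is not enough.
- **That primary-endpoint data will be lost unequally by arm.** No decline rate is given. The Arm A restriction comes from one site's costing, which says nothing about Spain or Italy and may not hold at other UK sites.
- **That losses could be large.** Losing 3, 6 or 10 people would mean 23%, 46% or 77% of about 13 UK romiplostim participants leaving over at most three blood draws.

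**Conclusion.** The concern holds for one table row. As written, declining only non-routine bloods ends scheduled follow-up, contrary to section 10 and to the table's treatment of other partial withdrawals. Because the lead site costs those samples for Arm A only, the rule could produce missing primary outcomes that are related to arm among UK participants.

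The effect is a risk of unknown and probably small size: about 1 to 3 people at 10-20% declining. This rests on 26 UK participants, 1:1 allocation and the lead-site sampling pattern; since 26 is a minimum, exposure could be somewhat larger. If outcomes are recovered from records, the loss could be close to nil. Should-fix: the effect is modest, but the change is simple and the loss cannot be fully made good later.

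**What to change.** - Remove the asterisk from the non-routine-blood row, so that scheduled visits and routine assessments continue unless consent to them is explicitly withdrawn.
- Keep the asterisks on the further-visits and lost-to-follow-up rows. State in both that platelet counts, ITP treatments, bleeding and vital status continue to be collected from hospital records unless the participant uses the separate option to stop collection from medical notes.
- Reconcile the table with Main Protocol Section 8.

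The cost is a short edit to three rows and a little record abstraction by site staff, who already take resource-use data from hospital records under section 12.3.

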11.1 Trial Drug Supplies

Trial drug supply (Romiplostim and Dexamethasone) to UK participating sites will be triggered via the

CTR UK green light procedure. Upon receipt of the site set up documentation dossier, enough IMP for

full protocol treatment of 4 participants will be provided to the pharmacy at the address provided to

CTR. Site will not be activated for recruitment until Site has confirmed receipt of trial IMP. IMP

resupply will be upon request by Site as required on an adhoc basis following the Sponsor re-supply

procedure.

11.2 Emergency Treatment With Dexamethasone

The use of commercial dexamethasone from UK hospital stocks will be permitted for up to 3 days only

following date of trial registration as emergency care whilst study eligibility is assessed and labelled

study medication is assigned. Other types of ITP pre-treatment, e.g. prednisolone, are prohibited.

11.3 Self-Administration of Drugs

See Section 7 of the Romiplostim Summary of Product Characteristics (SPC) for instructions for

preparing and giving an injection of Romiplostim. The first injection of Romiplostim must be

administered by the Site. Sites must ensure that participants have received training in self-

administration of Romiplostim and Dexamethasone (table) as per the main Protocol and local hospital

procedural requirements, and are comfortable with self-administration, prior to permitting self-

administration by the participant at home. The local green light for self-administration must be

evidenced in the participants hospital notes.

11.4 IMP Accountability

The CTR will be responsible for IMP accountability and management oversight in the UK via the EDC, remote and/or face-to-face site monitoring as documented in CTR Monitoring Plan, and liaison with drug manufacturers (Amgen and TAD Pharma), certifier (Alcura Health, Spain), importer and distributor (Alcura Health, UK), Site, and Sponsor.

Sites are responsible for documenting local IMP accountability via the EDC following instructions provided by the Sponsor.

11.5 IMP Storage Conditions and Temperature Monitoring

Refer to the Main Protocol for the IMP temperature monitoring and reporting procedure and below for UK storage and monitoring requirements:

IMP	Storage conditions	Site temperature monitoring
Dexamethasone (blister pack of 12 tablets for oral administration)	Below 25°C (as per trial drug label and contrary to SPC guidance - due to recent EU high summer temperatures).	During storage at site via local temperature monitoring.
	In original packaging to protect from light and humidity.	
Romiplostim * (white lyophilised powder for injection)	2-8°C (fridge). Protected from light.	During transit via return of shipment temperature monitor device.
Refer to the Main Protocol for Romiplostim reconstitution guidelines and permitted storage conditions and durations.		During storage at site via local temperature monitoring.

Temperatures will be logged at site using the RODEX Temperature Log provided in Site Pack where applicable.

Refer to the RODEX IMP Accepted Storage Conditions April 2023 document provided in the Site Pack for permitted storage condition deviations.

Non-permitted temperature deviations will be reported by Site on the RODEX Temperature Deviation Form provided in Site Pack. Forms should be emailed directly to Sponsor Trial Team, copying in the

CTR Trial Team.

See Section 12.4 for UK Event Reporting Flow Diagram.

11.6 IMP Quality Complaint Reports

Refer to the Main Protocol for the IMP quality complaint monitoring and reporting procedure.

See Section 12.4 for Uk Event Reporting Flow Diagram.

12 Samples, Visits, Assessments, Questionnaires and Health Resource

Utilisation

For full details refer to Section 10. Study Schedule of Main Protocol. Participants will remain on study

and in follow up for up to two years.

12.1 Study visits, assessments, and samples

No urine samples will be collected above and beyond those collected for UK routine care.

Routine blood sample collections, visits, and assessment requirements vary for the UK RODEX patient

cohort dependent on local hospital differences in ITP-treatment practices permitted under UK NICE

ITP Treatment guidance: https://bnf.nice.org.uk/treatment-summaries/immune-thrombocytopenic-

purpura/. The number and frequency of study-specific visits for the collection and assessment of

RODEX trial-specific blood samples will be marginally higher than routine care at most, and vary across

different, UK participating sites.

SOECAT costs associated with routine and research visits, assessments and samples are based on local

practice at the lead UK participating site (University Hospitals Bristol and Weston NHS Foundation

Trust); collection of up to three new blood samples above and beyond routine care from participants

assigned to Arm A (ROM+DEX) only during weeks 9-15 for clinical trial assessment purposes only.

Local differences to the lead UK Site procedure must be documented on the site registration form and

discussed with the UK National Coordinator prior to site set up and site green light approval.

All research and/or routine samples will not be transferred outside of the collecting host NHS

organisation and will be destroyed immediately following analysis following local policies and

procedures.

Page 25 of 40

RODEX UK Protocol Addendum V2.0 17.08.2023 FINAL Authorised CLEAN TPL/003/1 v5.0, 26/10/2022

Responsibility for sample collection resides with the Sponsor. For avoidance of doubt, the research will be registered on the UK National Coordinator's Human Tissue Authority (HTA) Register (Holding Number: 702).

12.2 Quality of Life Questionnaires

Three validated quality of life questionnaires (SF-36, FACIT-Fatigue Scale, and ITP Patient Assessment Questionnaire (ITP-PAQ), will be completed by each participant at five different time points from baseline to end of treatment as specified in the Main Protocol and for study purposes only. Questionnaires will be provided to participants by site as PDFs. Data entered on completed questionnaires will be remotely entered on the EDC System by Sites.

12.3 Health Resource Utilisation (HRU)

Data associated with health resource utilization will be collected from hospital records and entered on the EDC by Sites, supported by discussion with patient at trial visits where applicable.

12.4 Bleeding Events

Bleeding will be assessed by Site at every visit. Events will be assessed using WHO grading. ITP-specific bleeding using the ITP-BAT tool at the timepoints specified in the Main Protocol. All bleeding data will be entered remotely on the relevant section of the EDC System by Sites.

12.5 Patient Travel Expense Claims

Participants may claim travel expenses incurred for any study visit deemed by the site PI to be above and beyond local routine care as pre-agreed with the National Coordinator during site set up and in compliance with the reimbursement criteria, limits and process specified in the mNCA.

13 Safety Reporting

Refer to Main Protocol for full pharmacovigilance definitions and reporting procedures. Safety

reporting responsibilities of individual parties are summarised below.

The site is responsible for assessing all locally incurred UK safety and quality events and reporting

them directly to the Sponsor at the email address specified in the Main Protocol:

Email address for reporting safety and quality complaint events:

Unidad de Investigación Clínica y Ensayos Clínicos

Hospital Universitario Virgen del Rocío

Dpto. Farmacovigilancia

Email: [contact]

[name]

[name]

[contact]

[contact]

The Sponsor has delegated overall responsibility for centrally documenting SAEs and reporting of

safety events to the Pharmacovigilance Department, HUVR, Spain.

The Sponsor has delegated some UK safety reporting activities to the CTR as specified below and

documented in the CTR UK RODEX Safety Management Plan.

13.1 Reference Safety Information (RSI)

Reference Safety Information (RSI) will be reviewed regularly by the Sponsor. Refer to the main

Protocol for a list of documents and sections to be used as the RSI for the purpose of site assessment

of safety events. Refer to Amgen Risks and Discomforts Letter and document for recent

manufacturer's information about risks and discomforts associated with Romiplostim.

Page 27 of 40

RODEX UK Protocol Addendum V2.0 17.08.2023 FINAL Authorised CLEAN

TPL/003/1 v5.0, 26/10/2022

13.2 SAE and Quality Complaints Reporting

See Main Protocol Section 11 for SAE and Quality Complaint reporting procedures.

Serious Adverse events (SAE) should be graded using the NCI Common Terminology Criteria for Adverse Events (CTCAE) Version 5.0 and reported using the RODEX SAE Reporting Form.

The PI (or delegated medically qualified doctor from the trial team) should sign and date the form following procedures specified in the Main Protocol to acknowledge that he/she has performed the seriousness and causality assessments. Investigators should also report SAEs to their own health boards or trust in accordance with local practice.

All adverse events should be reported from time of signature of informed consent, throughout the treatment period up to, and including 30 days after the participant receives their last dose of the IMP. Serious adverse reactions (SARS; such as long term side effects of trial treatment under investigation) should continue to be reported until the end of follow up as defined in the protocol.

The participant will be identified on the SAE form by trial number, age (year/month/day), age group, full date of birth and (if applicable) full date of death only. The participant's name (or any other personal identifiers) should not be used on any correspondence with the Sponsor and/or CTR, i.e. reported in pseudonymised format. The participant will be identified to the CTR via trial number only.

Minimum reporting data fields and reporting timeframe restrictions are specified in the Main Protocol.

Sites must respond to and clarify any queries raised by the Sponsor on any reported SAEs and report any additional information as and when it becomes available through to the resolution of the event. Additionally, drug companies may request additional information relating to any SAEs/SARs and the site should provide as much information as is available to them in order to resolve these queries.

